The starting dose, titration schedule and target dose were selected based on safety, tolerability and efficacy data reported in previous studies using cannabinoids to treat pain (Langford et al., 2013; Portenoy et al., 2012; Johnson et al., 2010). Adverse effects will be inventoried at each study visit. If the patient or investigator feel that the higher study drug dose is causing troublesome side effects, the dosage may be lowered. Food intake can affect systemic exposure of cannabinoids (Zgair et al. 2016). Subjects will be advised to schedule their dose at a similar time every morning after breakfast to maintain similar systemic exposure throughout the study. Regular reminders will be provided to subjects to ensure they are taking the study drug post-meals. During study visits when drug is administered, subjects will be provided with a standardized FDA high-fat, high-calorie meal prior to taking the study drug.

DOSE TAPER AND WASHOUT

After completing a 2-week course on 15/300 mg/day of THC/CBD or placebo, subjects will return on this dose for assessment and completion of the various measures detailed in Appendix 1. After completion of this visit, subjects will taper from the treatment gradually over 1-week, in similar fashion to the dose titration up to the target dose. Subjects will then complete a 3-week washout period prior to being crossed-over to the alternate arm. This is to allow subjects to return to their baselines. The duration selected is conservative and takes into consideration the known elimination half-life of THC/CBD.

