9.7 Sample Size Estimation

A power analysis was performed to estimate the minimum number of subjects for enrollment. We assumed the following: Significance (p<0.01 or p<0.05, corrected), Power=0.80, minimum expected group difference of 15%, and an estimated standard deviation of 10%. Based on these assumptions, we will require a minimum of 14 participants to complete the study. For purposes of this study, 16 subjects will be enrolled and will complete all aspects of this study. To account for drop-outs due to various causes, we plan to have an accrual ceiling of 20 subjects.

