14. POTENTIAL RISKS

GENERAL ADVERSE EFFECTS

The risks and discomforts known to occur from the use of cannabis include but may not be limited to the following: coordination difficulties, dizziness, lightheadedness, eye irritation, increased heart rate (rapid heart beat), decreased blood pressure (low pressure of blood within arteries), sedation (sleepiness), feeling high, reversible effects on your appetite, mood, memory (ability or recall) and judgment (capacity to form an opinion). Specific mood changes may include anxiety, paranoia, and unusual, disturbing thoughts. Individual response to cannabis varies widely.

DEPENDENCE

Few Cannabis users develop dependence. With prolonged use, individuals may experience withdrawal symptoms such as irritability, restlessness, mild agitation, cramping, nausea, vomiting, sleep disturbances, and loss of appetite. Based on the dose of CBD and THC in TILRAY TN-CT120LM (FDA IND#137400), we do not anticipate symptoms of dependence or withdrawal, but will monitor for them nonetheless.

SOCIAL

Subjects are also informed that THC and CBD can be found in the body days or weeks after exposure, leading to a theoretical risk of a positive drug test should the subject be seeking employment, or undergoes testing as a part of their employment.

CARDIOVASCULAR

While the use of one of the cannabinoids (THC) found in the investigational drug is a rare trigger of cardiovascular events, there may be a significant increase in the rate of cardiovascular events (e.g. heart attack) for 1 hour following the use of cannabis.

REPRODUCTIVE RISKS

While THC and CBD are not known to cause birth defects, the investigators do not wish to expose the unborn child to any unnecessary medications, so subjects who are pregnant or unwilling to use a contraceptive during the course of the study will be excluded. A urine pregnancy test will be performed and confirmed negative before women of childbearing potential may participate in the study.

BLOOD SAMPLING

Since a blood sample will be collected at required study visits, subjects are informed about the risks of pain, discomfort, redness, bruising, infection and/or irritation at the needle insertion site, and rare risks of fainting, dizziness, and lightheadedness that may occur.

QUESTIONNAIRES AND SCALES

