APPENDIX 1: STUDY OVERVIEW

EVENT	VISIT 0: SCREENING	VISIT 1: DOSE TITRATION	VISIT 2: PK	VISIT 3: PK	TREATMENT PHASE	VISIT 4: ASSESSMENT	TAPER	WASHOUT	VISIT 5: DOSE TITRATION	VISIT 6: PK	VISIT 7: PK	TREATMENT PHASE	VISIT 8: ASSESSMENT	TAPER	TELEPHONE FOLLOW-UP	TOTAL DAYS
TOTAL DAYS	0	ų	5	1	16	1	5	22	ų	5	1	16	1	5	1	77
DAY NUMBER (±3)	0	1	3	6		22	23	28	50	52	55		71	72	77	
Consent	х															
Neurological Exam	х					x							х			
Vital Signs	х	х	Х	x		х			х	х	x		х			
TETRAS (video)	х					х							х			
Spirography	Х					X							Х			
Accelerometry	Х					Х							Х			
CGI/PGI						Х							Х			
PRO-CTCAE	х	x	х	x		х			x	х	x		х		х	
C-SSRS	Х					Х							Х		Х	
Lab Testing - pregnancy, CBC, CMP, Drug screen	x					x							x			
EKG*	x	x	x	x		x			x	x	x		x			
PK Sample(s)			Х	x		X				x	х		х			

* EKG at screening, then post-dose at each subsequent visit.

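### The only safety contact after Visit 8 is pinned to day 77, and because Section 9.3 and Appendix 1 disagree on taper length, it may fall before, on or just after the last capsule

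*Combined protocol and SAP*

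**What the plan says.** Section 9.3 (Dose Taper and Washout) says that after the assessment visit "subjects will taper from the treatment gradually over 1-week, in similar fashion to the dose titration up to the target dose". It continues: "Subjects will then complete a 3-week washout period prior to being crossed-over to the alternate arm".

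Appendix 1 places Visit 8 on day 71, the start of the second taper on day 72, and the column headed "TELEPHONE FOLLOW-UP" on day 77. Day numbers carry a window of plus or minus 3 days. The call has PRO-CTCAE and C-SSRS marked and nothing else. No column follows it, and no period for reporting adverse events after the last dose is stated elsewhere.

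Section 14 (Dependence) lists withdrawal symptoms and, for the doses in this study, says "we do not anticipate symptoms of dependence or withdrawal, but will monitor for them nonetheless".

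**The concern.** A contact meant to pick up withdrawal or late adverse effects has to come after dosing has stopped. Here the date of the call is fixed, but the date of the last capsule depends on which part of the protocol is followed.

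In Period 1 the disagreement hardly matters, because a washout follows: 5 + 22 = 27 days in Appendix 1 against 7 + 21 = 28 days in Section 9.3. In Period 2 no washout follows, so the taper length alone decides whether the last safety contact is made on or off drug.

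At stake is the tolerability record under Aim 2, and whether the schedule delivers the withdrawal monitoring that Section 14 describes.

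**Working it through.** **Inputs.** From Appendix 1: Visit 4 on day 22, first taper from day 23, washout from day 28, Visit 5 on day 50, Visit 8 on day 71, second taper from day 72, call on day 77, window plus or minus 3 days. From Section 9.3: taper of 1 week, taken as 7 days. The last taper day is taken as the last dosing day.

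**Reproducing the plan's total.** Successive differences of the day numbers, with 1 day for the call itself, give 2 + 3 + 16 + 1 + 5 + 22 + 2 + 3 + 16 + 1 + 5 + 1 = 77, the stated total. The taper block is 77 − 72 = 5 days, so Appendix 1 is consistent with itself on a 5-day taper.

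**Call relative to the last taper day, Visit 8 held at day 71.** Last taper day = first taper day + length − 1. Offset = call day − last taper day.

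| Reading | Last taper day | Call on day 74 | Call on day 77 | Call on day 80 |
|---|---|---|---|---|
| Appendix 1: 5 days from day 72 | 72 + 5 − 1 = 76 | −2 | +1 | +4 |
| Section 9.3: 7 days from day 72 | 72 + 7 − 1 = 78 | −4 | −1 | +2 |
| Section 9.3: 7 days counted from day 71 | 71 + 7 − 1 = 77 | −3 | 0 | +3 |

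At the nominal day, no reading gives more than 1 day off drug. At day 74 every reading puts the call before the end of the taper.

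**If Visit 8 also uses its window** (days 68 to 74) and the taper starts the day after it, the offset is call day − (Visit 8 day + 5) or call day − (Visit 8 day + 7). The extremes are:
- Visit 8 on day 74 and call on day 74: 74 − 79 = −5, or 74 − 81 = −7.
- Visit 8 on day 68 and call on day 80: 80 − 73 = +7, or 80 − 75 = +5.

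So the off-drug interval is not controlled by the schedule.

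**Comparison with Period 1.** The first taper ends on day 23 + 5 − 1 = 27, or on day 23 + 7 − 1 = 29 if it lasts a week. Visit 5 comes 50 − 27 = 23 or 50 − 29 = 21 days later, with PRO-CTCAE, vital signs and EKG marked but no C-SSRS. Between Visit 4 and Visit 5 (50 − 22 = 28 days) Appendix 1 schedules no contact. In Period 2 the call comes 77 − 71 = 6 days after Visit 8.

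**The case against.** The strongest reply is that the mismatch may be loose wording. Section 9.3 likens the taper to the titration, and in Appendix 1 the titration runs from day 1 to day 6, which is five days below the top step and matches a 5-day taper. Appendix 2, which holds the dosing plan, is not readable in the text available here and may settle the date of the last capsule. That stands as a reason not to assert that the call precedes the last dose. It does not remove the point: even on the 5-day reading the nominal off-drug interval is 1 day, and the window allows it to be negative.

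Second, the call does monitor something. It comes at about the end of the taper and includes PRO-CTCAE and C-SSRS, so symptoms that begin during the taper can be recorded. Section 15 also provides for suicidal ideation reported by telephone between visits, and the consent form gives study contacts. This is right. Later events are not necessarily lost; they depend on spontaneous reports.

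Third, a reader might infer that follow-up is worse in Period 2 throughout, and that the drug-placebo comparison is biased. The documents do not support that. Visit 5 has no C-SSRS, and for symptoms during or just after the taper Period 2 is followed more closely than Period 1. Period 1 is better only for late adverse events. If the two sequences are balanced (an assumption; the allocation ratio is not given), the difference lies between periods and applies to drug and placebo alike. It reduces what can be seen of late effects but does not favour either treatment.

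Fourth, a reader might take the washout, or the statement that "THC and CBD can be found in the body days or weeks after exposure", as the protocol's own standard for safety follow-up. Neither is. The washout serves the cross-over and is described as conservative, and the statement on persistence appears under social risks and concerns drug testing.

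**Conclusion.** The point holds as a scheduling fault of limited size. The only contact after Visit 8 falls nominally 1 day after, on, or 1 day before the last taper day, and with Visit 8 on day 71 the window widens this to between −4 and +4 days across the readings. Adverse effects and withdrawal after dosing stops in Period 2 are therefore not systematically collected. With 16 completers and equal sequences (assumed), about 16 / 2 = 8 subjects would take active drug in Period 2.

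It would go too far to say that the monitoring described in Section 14 cannot be met: that section does not expect withdrawal and sets no duration, and the call covers the taper. The spirography primary outcome is measured by Visit 8 and is untouched. The result rests on the Appendix 1 day numbers, a 7-day week, and the last taper day being the last dosing day. Nothing here judges which taper length is right.

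**What to change.** Three linked edits:

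1. Reconcile the taper length between Section 9.3 and Appendix 1, for both periods, and check that Appendix 2 agrees.
2. Define the existing call, with PRO-CTCAE and C-SSRS kept, by the actual date of each subject's last capsule rather than by day 77, with a window that cannot open before that date. The sponsor should choose the off-drug interval and state the reason for it.
3. Update the day-77 column and the 77-day total to match.

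The Appendix 1 washout should not simply be carried over as the interval. It would put the call at about day 76 + 22 = 98, leaving 98 − 71 = 27 days after Visit 8, covering the whole taper and the first weeks off drug, with no scheduled contact.

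The cost is a protocol amendment and slightly longer participation by telephone, with no added visit or assessment.

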9.4 Assessment Measures

DIGITAL SPIROGRAPHY

This functional measure of kinetic tremor in subjects with ET has been validated by a group at NINDS, including [name]. In this technique, the subject is asked to draw a spiral between the loops of a pre-printed spiral with an unsupported hand, proceeding from inside the figure to outside. This measure offers an objective measure of functional tremor, and may enable detection of efficacy with fewer subjects (Haubenberger et al.,

2011). As this methodology is recent, it has not yet found widespread application ET clinical trials. Subjects with severe tremor who have difficulty keeping the inking stylus in contact with the paper are not suited for this test. Based on our experience, we consider this scale to be appropriate as a primary outcome measure.

ACCELEROMETRY

This functional measure of tremor allows objective measurement of postural tremor. During this task, subjects are asked to maintain each arm in an isometric posture with the arm in a 'winged' position in front of the chest. Tri-axial accelerometers are used to collect the tremor frequency and magnitude. Tremor severity is derived from the time domain of a Fourier transformation. This measure allows for standardization across time and 1-minute of data is collected for each limb to minimize variability.

TETRAS

This scale evaluates tremor of various body parts during postures, kinesis and tasks. Items are scored from 0 to 4, with 4 representing the highest degree of severity. The maximum score is 64 (Elble et al., 2012). Although this scale was recently published, it is a refinement of the long-used Fahn-Tolosa-Marin scale. Based on the authorship, this scale has clearly received widespread endorsement from the opinion leaders in the field of essential tremor. To achieve maximum credibility with any result from this clinical trial, it is appropriate to include this scale as a second primary measure. One difficulty with on-site blinded examiners is that they may be prone to placebo effects in their ratings, as they are aware which visit is baseline and which is the treatment visit, although the latter may be with placebo or active drug. To eliminate such order effects, we will videotape the subject undergoing this rating and provide the videos to a minimum of two blinded raters unfamiliar with which visits are baseline and treatment visits.

GLOBAL IMPRESSION OF CHANGE

This is a standardized and commonly used 7-point scale in which both the subject (PGI) and blinded clinician (CGI) rate the degree of change from baseline.

PATIENT REPORTED OUTCOMES OF THE COMMON TERMINOLOGY CRITERIA

All adverse events will be assessed and recorded using the Patient Reported Outcomes of the Common Terminology Criteria for Adverse Events (PRO-CTCAE) version 1.0. This is a standardized tool for identifying adverse events across all organ systems and includes severity classification.

PHARMACOKINETIC ANALYSES

Established nonlinear mixed-effects modeling methods will be used to evaluate the population pharmacokinetic and pharmacodynamic properties of CBD, THC, and 11-OH-THC. The correlation between plasma concentrations and/or PK parameters with demographic factors (age, sex, body size, race) will be investigated, along with analysis of any relationship between exposure and the resulting efficacy and/or safety response. Different relationships (linear, log-linear, Emax and Sigmoidal Emax) will be explored to correlate exposure with pharmacodynamic metrics (assessment measures of tremor). In addition, as prior studies have shown a hysteresis between THC plasma concentration and drug effect, we anticipate modeling the effect(s) using a hypothetical effect compartment, i.e. $dCe/dt = ke0 \cdot (Cp - Ce)$, where Cp is the plasma concentration, Ce is the concentration in the effect compartment, and ke0 is the a first-order rate constant describing transport into the effect compartment. The final population pharmacokinetic model will be used to perform Monte Carlo simulations to determine the distribution of CBD, THC, and 11-OH-THC at various oral doses.

COLUMBIA-SUICIDE SEVERITY RATING SCALE (C-SSRS)

Suicidality will be assessed by trained study personnel using the C-SSRS (Posner et al. 2011). The C-SSRS is a standardized suicidal rating system conducted by a certified rater. The interview measures presence of suicidality and consists of four categories: suicide ideation, intensity of ideation, suicidal behavior and answer

for actual attempts only. This scale will be used for screening as well as to assess for the occurrence of any suicidal ideation and/or behavior during the study.

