6. SPECIFIC AIMS

The present study seeks to assess the efficacy and tolerability of TILRAY TN-CT120LM (FDA IND#137400), a pharmaceutical-grade formulation containing THC and CBD, vs. placebo in an Essential Tremor patient population. The study is intended to collect pilot data to determine whether larger studies are warranted and assist in their future design.

Aim 1: To determine if short-term exposure to orally administered THC/CBD improves tremor amplitude in ET patients. Hypothesis 1: ET patients receiving THC/CBD orally will have reduced peak tremor power (compared with their own baseline measures) by accelerometry and spirography vs. placebo.

Aim 2: To determine acute and short-term tolerability of orally administered THC/CBD. Hypothesis 2: ET patients receiving THC/CBD orally will be associated with more frequent ratings of sedation on the Common Toxicity Criteria compared with placebo.

Aim 3: To characterize the relationship between THC/CBD exposure with clinical response (i.e. tremor amplitude) to define a plausibly useful dose range for evaluation in future confirmatory clinical trials.

BACKGROUND AND SIGNIFICANCE 7.

7.1 There is a great medical need for a more effective treatment for essential tremor.

Essential tremor (ET) is traditionally defined as bilateral, generally symmetric postural and kinetic tremor of the upper extremities that is not attributable to identifiable causes, and has been present for at least 5 years. A meta-analysis of prevalence studies indicates that 0.4 to 0.9% of the general population has ET. The figure rises to 4.6 to 6.3% among those 65 years or older (Louis and Ferreira, 2010). ET is a common cause of embarrassment, social withdrawal, disability, and loss of occupation.

The most commonly utilized medications for ET are propranolol, primidone, topiramate, gabapentin, and benzodiazepines. Unfortunately, the long-term efficacy and tolerability of current medications leave much to be desired. If one surveys hundreds of ET patients, it is found that one-third have stopped all ET medications, even those with the most severe tremor. In other words, many of the most disabled ET patients have abandoned the search for a drug that can help them. Over half the patients who try primidone, propranolol, diazepam or topiramate end up stopping them, and the percentage is higher with other anti-ET medications (Louis et al., 2010).

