7.4 Objective assessment of efficacy can be performed with a relatively small number of ET subjects Tremor is reliably elicited during posture and movement in persons with ET, thus permitting assessment of efficacy with relatively few subjects compared to other medical or neurological conditions that are characterized by intermittent events. Cross-over Phase 2 trials for ET that use rating scales typically employ 20 to 60 subjects. Moreover, the use of digital spirography and accelerometry provide greater power at smaller sample sizes, as these measures appear to be more sensitive and reliable than the use of rating scales. In the ET field, the standard is to include placebo in the first reported trial of a treatment. The reason for this is that in the 1980's and 1990's numerous open-label positive results could not be replicated in controlled trials. Given the paucity of new treatments for ET in the past 10 years, knowledge of a positive result with even a small trial will rapidly become disseminated within the ET community. It may be noted that none of the medications currently prescribed for ET are FDA-approved for that condition. A single positive Phase 2 study can result in a marketed drug gaining access to the \$5-15 billion global ET market.

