9.6 Outcome Measures

Primary Outcome Measures

The primary outcome measures will be change from baseline of tremor power by digital spirography for drug vs. placebo.

Secondary Outcome Measures

The secondary outcome measures will include the TETRAS, CGI, PRO-CTCAE, plasma concentrations of CBD/THC, Common Toxicity Criteria for adverse effects, and Columbia-Suicide Severity Rating Scale.

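### Section 9.4 makes TETRAS a second primary measure, 9.6 makes it secondary to spirography, and no single alpha is chosen, so Aim 1 has no fixed reading

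*Combined protocol and SAP*

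**What the plan says.** Section 9.4 describes the instruments and gives two of them primary status. Of digital spirography it says "we consider this scale to be appropriate as a primary outcome measure". Of TETRAS it says "it is appropriate to include this scale as a second primary measure", for the sake of the credibility of the result.

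Section 9.6, which designates the outcomes, says otherwise: "The primary outcome measures will be change from baseline of tremor power by digital spirography for drug vs. placebo", and then "The secondary outcome measures will include the TETRAS" along with other measures. Accelerometry is in neither list, although 9.4 describes it and Appendix 1 schedules it. Hypothesis 1 in section 6 expects reduced tremor power "by accelerometry and spirography vs. placebo". Section 9.1 counts both safety and efficacy among the primary endpoints, while 9.6 places the safety measures with the secondaries.

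Section 9.7 assumes "Significance (p<0.01 or p<0.05, corrected), Power=0.80, minimum expected group difference of 15%, and an estimated standard deviation of 10" percent, and arrives at a minimum of 14 completers with 16 planned. Section 9.8 plans paired t-tests across the outcome measures and states no alpha and no multiplicity rule.

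**The concern.** Sections 9.4 and 9.6 cannot both be followed, and nothing in the document says which prevails. If spirography and TETRAS point different ways, each section supports a different conclusion on Aim 1. If the p-value falls between 0.01 and 0.05, the text does not say whether the aim is met, because 9.7 names two levels as planning assumptions and 9.8 names none.

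This matters even in a small study because of its declared purpose: "The study is intended to collect pilot data to determine whether larger studies are warranted". A reading of success that can be chosen after unblinding is a weak basis for that decision.

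**Working it through.** **Side by side**

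| Measure | Hypothesis 1 | 9.4 | 9.6 |
|---|---|---|---|
| Spirography | tested | primary | only primary |
| TETRAS | not named | second primary | secondary |
| Accelerometry | tested | described, no rank | not listed |

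The TETRAS row is a contradiction. The accelerometry row is an omission, because the secondary list in 9.6 is worded as inclusive.

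**Inputs.** From 9.7: difference 15 points, SD 10, power 0.80, alpha 0.05 or 0.01, minimum 14 and planned 16 completers. From 9.8: paired t-test. Assumed, because the plan is silent: two-sided tests, the correlation ρ between conditions, and a correlation of 0 to 0.7 between the two tremor measures.

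**Reproducing the 14**
- Two-group normal formula at 0.05: n per group = 2 × 10² × (1.960 + 0.842)² / 15² = 6.98, so 7 per group and 14 in total.
- Paired t-test, with SD of the difference = 10 × √(2(1 − ρ)), smallest n with power of at least 0.80:

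| SD of difference | 0.05 | 0.01 |
|---|---|---|
| 10 (10% is already the SD of the difference, or ρ = 0.5) | 6 | 9 |
| 14.14 (10% per condition, ρ = 0) | 10 | 14 |

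So 14 is reproduced either by a two-group formula at 0.05, which does not match the paired test in 9.8, or by a paired test at 0.01 with an SD of the difference of 14.1%. The text does not say which was used.

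**Power at the stated alphas.** Paired noncentral t, with standardised effect 15/10 = 1.5 or 15/14.14 = 1.06:

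| n | Effect | 0.05 | 0.01 | Gap |
|---|---|---|---|---|
| 14 | 1.5 | 0.999 | 0.989 | 0.010 |
| 14 | 1.06 | 0.956 | 0.809 | 0.147 |
| 16 | 1.5 | 0.9999 | 0.9967 | 0.003 |
| 16 | 1.06 | 0.977 | 0.882 | 0.095 |

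The gap is the share of trials whose verdict depends on which alpha is meant: 0.3% or 9.5% at n = 16.

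**Split between spirography and TETRAS.** This is at n = 16 and 0.05, with the same effect on both. For independent measures the probability is 2 × power × (1 − power). At 1.06 that is 2 × 0.977 × 0.023 = 4.5%. Simulated trials give 3.8% and 3.2% at correlations of 0.5 and 0.7 between measures. At 1.5 it is about 0.03% throughout.

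**False-positive rate if either measure at an uncorrected 0.05 could carry the claim.** Independent: 1 − 0.95² = 9.75%. Simulated at correlation 0.7: 8.5%.

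**The case against.** The strongest reply is that 9.6 is the section that designates outcomes and 9.4 only explains the instruments, so most readers would follow 9.6. That is a fair account of how the text would usually be read, and it is why the fix lets 9.6 govern. It does not remove the conflict: 9.4 gives its own reason for a second primary, and no sentence ranks the sections.

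A second reply concerns size. Appendix 1 schedules spirography at screening and Visits 4 and 8 only, so both changes share one baseline. With equal variances and equal correlations between visits (an assumption), two such changes correlate at 0.5. A per-condition change SD of 10% then gives an SD of the difference of 10%, where disagreement and dependence on alpha are negligible. This stands, and the zero-correlation figures should be read as near the pessimistic end.

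Three stronger readings are tempting and unsupported.
- A reader might infer that 14 is too few. At the stated alphas power is at least 81% on either reading of the SD, so an undefined SD is a reporting gap only.
- A reader might infer that the measures would often disagree. Assuming a true effect of only 0.75 SD on both raises disagreement to 18 to 32% and the share decided by alpha to 26%, but that effect is not in the plan. It is essentially the effect that 16 completers detect with 80% power at 0.05.
- A reader might infer an inflated error rate. That needs a rule under which either measure suffices, and the plan states no such rule.

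**Conclusion.** The contradiction over TETRAS is real and should be fixed. Around it stand the gap for accelerometry, the different account of the primary endpoints in 9.1, and two alphas with neither chosen. Together they leave Aim 1 without a fixed reading in two situations: a split between spirography and TETRAS, and a p-value between 0.01 and 0.05.

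On the plan's inputs at n = 16 these situations range from negligible (under 0.1% and 0.3%) to moderate (about 3 to 4.5% and 9.5%), depending on what the 10% SD refers to. The range rests on two-sided paired t-tests, equal effects on both measures, and assumed correlations that the documents do not give. The conflict itself does not depend on those figures. The undefined SD and the unexplained word *corrected* are missing detail and are not errors in the sample size.

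**What to change.** Make these changes, dated before unblinding.

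1. Let 9.6 govern. Edit 9.4, 9.1 and Hypothesis 1 so that the drug-versus-placebo comparison of spirography alone decides the efficacy primary, and list TETRAS and accelerometry as secondary in 9.6. The ground for this is 9.6 itself. Section 7.4 says that "these measures appear to be more sensitive and reliable than the use of rating scales", but it speaks of spirography and accelerometry together, so it supports preferring them to TETRAS and does not rank one above the other.
2. If TETRAS is kept as co-primary, state the rule: both measures at the full alpha, or either at half.
3. Choose one two-sided alpha, use it in both 9.7 and 9.8, and explain or delete *corrected*.
4. As a minor note when 9.7 is next edited, say what the 10% is the SD of and restate the calculation for the paired test.

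The cost is wording in sections 6, 9.1, 9.4, 9.6, 9.7 and 9.8; enrolment is unchanged. The downside is that TETRAS loses its co-primary label. Keeping it is affordable at 0.05: with 14 completers and an SD of the difference of 14.1%, power is 91% per measure at 0.025, or 91 to 93% for both at 0.05. With 0.01 as the chosen alpha and either measure at 0.005, power per measure is 71% at 14 completers and 81% at 16, so the alpha and the co-primary rule should be settled together.
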